surgical trauma and postoperative pain, low bleeding complication rates, shorter hospital length of stay and increased patient satisfaction.^{1 2} Robotic-assisted surgery (RAS) has emerged as an alternative minimally invasive surgical option, providing increased ergonomics, magnification of the surgical field, greater amplitude of movement and higher precision.³

Despite the growing applicability of RAS, the need of pneumoperitoneum and steep head-down (Trendelenburg) position could have a marked influence on patients respiratory mechanics. Indeed, this could lead to increased intra-abdominal pressure and cephalic elevation of the diaphragm, decreasing the compliance of the respiratory system and tidal volume, as well as increasing the plateau and peak pressure.⁴⁻⁸

Postoperative pulmonary complication (PPC) usually occur between 5 and 7 days after surgery and include the development of respiratory events, such as acute respiratory failure, acute respiratory distress syndrome (ARDS), pneumonia, prolonged or unplanned mechanical ventilation, reintubation, hypoxemia, atelectasis, bronchospasm, pleural effusion, pneumothorax and respiratory depression.⁹ Approximately, 5% of patients submitted to surgery develop at least one PPC during the follow-up, resulting in longer hospital length of stay and higher mortality rates.¹⁰ The changes in respiratory mechanics induced by the surgical positioning and by the degree of pneumoperitoneum during RAS could increase the risk of PPC in this group of patients. Nevertheless, there are currently insufficient data to guide the best ventilatory strategy during RAS, with some reports suggesting that ventilatory parameters should be adjusted to maintain normocapnia, despite the associated need for high tidal volumes.^{8 11}

The aim of the AVATaR study is to investigate the incidence of PPC, characterise current ventilatory practices and evaluate the association between ventilatory parameters and outcomes in surgical patients undergoing general anaesthesia for RAS.

METHODS

Design

This is an international multicenter prospective observational study designed in accordance with the declaration of Helsinki, registered at www.clinicaltrials.gov (trial identification number NCT02989415).

Patient and public involvement

Patients or public were not involved in the study design.

Patient eligibility

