Consecutive patients undergoing mechanical ventilation for general anaesthesia for RAS will be consecutively included during a period of 1 month, to be defined by each of the participating centres. The need for informed consent is determined by the Institutional Review Board of each participating centre or country, following local regulations.

Inclusion and exclusion criteria

Patients fulfilling the following inclusion criteria are included: (1) age ≥ 18 years and (2) surgical procedures performed under general anaesthesia for RAS, including head and neck, chest, cardiac and abdominal surgeries. Patients submitted to procedures during pregnancy or outside the operation room are excluded.

Steps and data collection

Local investigators at each participating centres screen all patients submitted to mechanical ventilation during general anaesthesia for RAS during a predefined period of 1 month. PPC will be collected on day 0 (end of surgery until 11:59 pm) and on postoperative days 1, 2, 3, 4 and 5 (each day goes from 00:00 to 23:59). Data collection is finished on the day of hospital discharge or on day 5, for patients who remain hospitalised (figure 1). The start date for each participating centre is flexible and is determined together with the study coordinator.

Outcomes

The primary outcome is the incidence of PPC, defined as a collapse composite endpoint of: unplanned need for oxygen therapy (defined as supplementary oxygen used due to $\text{PaO}_2 < 60$ mm Hg or $\text{SpO}_2 < 92\%$ in room air in individuals with no prior pulmonary disease or $\text{SpO}_2 < 88\%$ in individuals with prior pulmonary disease), development of acute respiratory failure (defined as $\text{PaO}_2 < 60$ mm Hg or $\text{SpO}_2 < 92\%$, despite treatment with oxygen or need for non-invasive ventilation or unplanned continuous mechanical ventilation), development of pneumonia (defined by the presence of a new or progressive radiographic infiltrate in addition to at least two of the five clinical characteristics: fever $> 38^\circ\text{C}$, leucocytosis or leucopenia (leucocyte count $> 12.0 \times 10^9/\text{L}$ or $< 4.0 \times 10^9/\text{L}$, respectively),¹² development of ARDS (defined according to Berlin criteria)¹³ and/or development of pneumothorax (defined as the presence of air between the visceral and parietal pleura; diagnosis can be made by clinical examination and chest X-ray).¹⁴

[figure not shown]

Figure 1 Study flow chart.

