Intraoperative characteristics will be presented as shown in mock [table 2](#).

Ventilatory variables

Ventilatory variables and other interventions will be reported hourly for 6 hours and in four specific periods: (1) 5 min after induction and beginning of ventilation (T_1); (2) 5 min after CO_2 insufflation (T_2); (3) 5 min after definitive positioning (immediately before beginning surgery) (T_3) and (4) 5 min after removal of pneumoperitoneum and return to supine (T_4). Peak, plateau and driving pressure (defined as plateau minus positive-end expiratory pressure (PEEP)) and PEEP levels, tidal volume size, respiratory rate, fraction of inspired oxygen (FiO_2), static and dynamic respiratory system compliance, pulse oximetry (SpO_2), heart rate, mean arterial pressure and pressure of CO_2 insufflation over the four specific periods will be analysed using a mixed model with repeated measures and plotted in an interaction plot (mock [table 3](#)).

Primary outcome

The number of patients developing a PPC will be reported in absolute numbers and percentages (mock [table 4](#)). The impact of ventilatory variables on the development of PPC will be assessed using a generalised linear mixed-effect model. Relevant covariates included in the final multivariable model will be identified as those with $p<0.2$ in the univariable model (including centre as a random effect), clinical relevance and no statistical association with other relevant variables. In the final model, time of measurement will be included as a fixed effect together with the variables of interest and the centres and patients will be included as random effect. The linearity of each continuous predictor with the log odds outcome will be checked graphically and, if not present, a log-transformation will be performed. Pearson correlation coefficients will be used to assess collinearity between predictors. Since a high collinearity between peak, plateau and driving pressure is expected, the main model will consider the variable with the higher amount of measurements between peak or plateau pressure. Driving pressure will be considered in a sensitivity analysis, excluding PEEP, peak and plateau pressure. Finally, the intraclass correlation coefficient (ICC) will be assessed. The ICC represents the ratio of between-site variance to total variance, ranging from 0 to 1.

Secondary outcomes

Secondary outcomes will be reported as shown in mock [table 4](#).

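### The final ventilation-PPC model puts a patient random effect and a time term on a once-per-patient yes/no outcome, so its estimates depend on the software and can err in either direction

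*SAP*

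**What the plan says.** - **Outcome.** SAP, Outcomes: "The primary outcome is the incidence of PPC, defined as a collapse composite endpoint of" five listed complications. SAP, Steps and data collection, has PPC recorded by day from day 0 to day 5. SAP, Primary outcome, then counts patients with a PPC, so the analysed outcome is one yes/no per patient.
- **Exposure.** SAP, Ventilatory variables: "Ventilatory variables and other interventions will be reported hourly for 6 hours and in four specific periods" (T1 to T4).
- **Final model.** SAP, Primary outcome, uses a generalised linear mixed model. For the random part it states: "together with the variables of interest and the centres and patients will be included as random effect". For the time term it states: "time of measurement will be included as a fixed effect". The scale is logistic: "The linearity of each continuous predictor with the log odds outcome will be checked graphically".
- **Around it.** The univariable screening models name centre as random effect and no patient effect. A site ICC is to be reported, as site variance over total variance. SAP, Predefined statistical analysis plan, names R but no package, integration method or fallback.
- **Aim served.** The closing paragraph of the Introduction sets out to "evaluate the association between ventilatory parameters and outcomes in surgical patients undergoing general anaesthesia for RAS".

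**The concern.** A time-of-measurement term and a patient random effect both presuppose several outcome rows per patient. The collapsed PPC endpoint supplies one. The two can be combined only by copying a patient's PPC status onto every ventilatory reading. The outcome is then constant within patient, and a patient-level variance cannot be estimated sensibly from it. This is the final model for a stated aim, so at stake is whether any reported association, or absence of one, between ventilation and PPC reflects the data or the point at which an optimiser stopped.

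**Working it through.** The SAP gives no sample size, power or expected odds ratio, so there is no figure to reproduce. The check is whether the specified model can be estimated.

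**1. Possible layouts**

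| Rows | Consequence |
|---|---|
| One per intraoperative reading (natural reading) | PPC copied to each row, constant within patient |
| One per patient | Patient effect not identified; no time of measurement to enter |
| One per postoperative day | No longer the collapsed endpoint; in this section the repeated measurements are ventilatory readings |

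On the first layout, time cannot explain PPC, because every time point carries the same set of outcomes. Fitted alone, its coefficients are 0 with p = 1.

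**2. Why the patient SD runs away.** With patient SD σ, intercept σc and standard normal u, patient i contributes

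L_i = ∫ Π_j p_ij(u)^y_i [1 − p_ij(u)]^(1−y_i) φ(u) du, where logit p_ij(u) = σ(c + u) + βx_ij + time_j.

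Any finite σ gives some probability to a patient having both PPC and non-PPC rows, which never happens. As σ grows, with β and the time effects held finite, L_i tends to p^y_i (1 − p)^(1−y_i) with p = Φ(c). The exposure then drops out.

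**3. One simulated data set** (assumed: 300 patients, 4 rows, true odds ratio 1.5 per unit of patient-mean exposure; 41 events). The limit is 41·ln(41/300) + 259·ln(259/300) = −81.6 − 38.1 = −119.7.

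| Patient SD (fixed) | Log-likelihood | OR | Wald z |
|---|---|---|---|
| 0 | −465.7 | 1.56 | about 5.0 |
| 5 | −170.5 | 1.84 | 2.0 |
| 20 | −131.5 | 2.14 | 1.0 |
| 80 | −122.6 | 2.28 | 0.55 |

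R on the same data, with one patient-level covariate added:

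| Fit | Patient SD | OR | SE (log OR) | p |
|---|---|---|---|---|
| lme4 default, with centre (no convergence message) | 69 | 1.39 | 0.86 | 0.70 |
| lme4 nloptwrap, with centre | 74 | 1.31 | 4.4 | 0.95 |
| lme4 Laplace, no centre | 48 | 1.49 | 0.0017 | about 0 |
| lme4 9-point quadrature, no centre (no convergence message) | 219 | 1.39 | 1.13 | 0.77 |
| lme4 25-point quadrature, no centre | 62 | 1.41 | 0.001 | about 0 |
| glmmTMB, with centre | 732,085 | 0.02 | 6.6 | 0.56 |
| One row per patient, centre random | none | 1.97 | 0.223 | 0.002 |

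**4. Site ICC.** Across three lme4 optimisers the centre SD was 0.32, 1.53 and 3.33, with patient SD 69.18, 69.2 and 74.46. Taking π²/3 = 3.29 as residual variance (the SAP names no scale) and counting patient variance in the total:
- 0.10/(0.10 + 4785.9 + 3.29) = 0.00002
- 2.34/(2.34 + 4788.6 + 3.29) = 0.0005
- 11.09/(11.09 + 5544.3 + 3.29) = 0.0020

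Without patient variance in the total they are 0.10/3.39 = 0.03, 2.34/5.63 = 0.42 and 11.09/14.38 = 0.77. The one-row model gives 0.109/(0.109 + 3.29) = 0.03.

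**5. Repeated simulation.** Assumed: 500 patients, 4 rows, within-patient exposure correlation r from 0.5 to 1, PPC about 10%, with 5% also run because the Introduction reports that about "5% of patients submitted to surgery develop at least one PPC". The log-likelihood rose from SD 5 to 10 to 40 in 280 of 280 data sets, centre omitted.

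Default lme4 with centre (20 centres of 25 patients, centre variance 0.5 assumed, true OR 1.5, r = 0.7, 0.95 and 0.98, 8 data sets each) stopped at patient SD 70 to 75. It rejected in 0/24, against 17/24 for the one-row model, and gave a warning or message in 7/24. glmmTMB on 12 of these data sets stopped at 70 to 75 in ten. In the other two it ran to about 27,000 and 2.3 million, with OR above 10^14, where lme4 gave 1.64 and 1.21.

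With no true effect, 2 of 11 default lme4 fits including centre gave SE about 0.001 and p = 0, both with warnings. The other nine were null.

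**The case against.** **Scope.** The primary outcome is incidence, reported as counts and percentages. The model serves one of several aims in an observational convenience sample. That is true and limits the damage, but the model is the final one for that aim.

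**The layout is inferred.** The SAP never states the rows, and readings are also hourly, so four rows is an assumption. This stands. What is certain is that the two terms do not fit a once-per-patient outcome. The numerical behaviour illustrates one reading, and the absence of a finite maximum is shown numerically, not proved for every data set.

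**Stronger readings that a reader might infer.**
- *The model hugely inflates odds ratios.* With patient SD fixed at 40 and a patient-constant exposure, the median OR was 2,440 against 1.47 for one row. That is a point on a profile, on a patient-conditional scale. The usual conversion factor √(1 + 0.346σ²) is 23.6 at σ = 40, and ln 2,440/ln 1.47 = 7.80/0.385 = 20.3, so rescaling accounts for most of it. Rejections were 18 of 25 either way. Default lme4 medians were only 1.32 to 1.55.
- *The model always loses power.* At SD 40, rejections out of 25 against one row were 0 against 18 at r = 0.7, 10 against 20 at r = 0.95 and 18 against 18 at r = 1. With PPC 5% they were 0 against 13 (r = 0.7) and 6 against 12 (r = 0.95). The SAP gives neither r nor the package, so no single loss can be attributed to it.
- *False positives are safe.* In no-effect profiles at SD 40, none of 80 data sets rejected. Those profiles fix the SD, which an analyst would not do, and the 2 of 11 software fits with p = 0 contradict the reassurance.

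**One row per patient is not the only repair.** Correct. Pooled logistic regression on all rows with patient-clustered robust errors had 78% power against 78% for one row (r = 0.7, OR 1.5, 200 data sets). With no effect it rejected 8.0% against 5.5%. The Monte Carlo error is √(0.05 × 0.95/200) = 1.5 points, so the runs do not separate these clearly. Only naive errors on repeated rows are ruled out: in the 300-patient data set they gave SE 0.089 against 0.22.

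**Conclusion.** The rule is wrong as written and should be changed before analysis. A patient random effect and a time-of-measurement term do not belong in a model for one collapsed yes/no per patient, and no reading of the SAP rescues them. On the natural reading the odds ratio, standard error, p value and site ICC are set by software choices that the plan leaves open. On one data set p ran from about 0 to 0.95.

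The direction of error cannot be predicted. Most default lme4 fits produced a spurious null, but some fits gave near-zero standard errors even with no true effect. These figures rest on assumed sample size, event rate, effect, number of rows and correlation; the mechanism does not depend on their exact values.

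It does not follow that the study's primary result is unsound. PPC incidence, the centre-only screening models and the repeated-measures models with ventilatory variables as outcomes are unaffected.

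**What to change.** In SAP, Primary outcome:

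- Fit the PPC model with one row per patient.
- Enter each ventilatory variable as one prespecified patient-level summary (for example a time-weighted mean), or as its value at one named period. State whether T1 to T4 or the hourly readings supply it.
- Keep centre as the only random effect, delete the patient effect and the time term, and take the site ICC from this model, stating its scale.
- If repeated rows are preferred, drop the patient random effect, still account for centre, and use patient-clustered standard errors, never naive ones.
- Leave the repeated-measures models of the ventilatory variables as they are.

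The cost is SAP wording and analysis code, with no new data. The downside is small: the exposure summary must be chosen before results are seen. Separate models per period would add tests to a plan that does not adjust p values.

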(REDCap, USA) via the Internet at the Clinical Research Unit system of the Hospital Israelita Albert Einstein (the case report form is available in the online Supplementary data). The system has the following functions: patient registration, data input, data cleaning, audit trail and data export for statistical analysis. Local investigators enter the data directly into the system. Instructions for using the system are available to investigators at all times. Electronic files are archived in the Hospital Israelita Albert Einstein-based server in a secure and

Table 2 Intraoperative characteristics

| All patients (n=) | |
|---|---------------|
| Type of tracheal tube | |
| Simple endotracheal | n/Total (%) |
| Double-lumen endotracheal | n/Total (%) |
| Nasotracheal | n/Total (%) |
| Endobronchial tube | n/Total (%) |
| Endobronchial blocker | n/Total (%) |
| Type of anaesthesia | |
| Total intravenous | n/Total (%) |
| Volatile | n/Total (%) |
| Balanced | n/Total (%) |
| Use of antibiotic prophylaxis | n/Total (%) |
| Use of one-lung ventilation | n/Total (%) |
| Left lung ventilated | n/Total (%) |
| Right lung ventilated | n/Total (%) |
| Use of neuroaxial blockade | n/Total (%) |
| Epidural | n/Total (%) |
| Spinal | n/Total (%) |
| Combined | n/Total (%) |
| Use of Trendelenburg during surgery | n/Total (%) |
| Normal | n/Total (%) |
| Accentuated ($\geq 40^\circ$ of the bed) | n/Total (%) |
| Reverse | n/Total (%) |
| Surgical conversion | n/Total (%) |
| Conversion to open surgery | n/Total (%) |
| Conversion to laparoscopic | n/Total (%) |
| Use of carbondioxide insufflation | n/Total (%) |
| Abdominal | n/Total (%) |
| Thoracic | n/Total (%) |
| Mediastinum | n/Total (%) |
| Use of opioids | n/Total (%) |
| Short acting | n/Total (%) |
| Long acting | n/Total (%) |
| Both | n/Total (%) |
| Use of neuromuscular blocking agents | n/Total (%) |
| Neuromuscular blockade monitoring | n/Total (%) |
| Reversal of neuromuscular blockade | n/Total (%) |
| Residual curarisation | n/Total (%) |
| Total fluid intake, mL | Mean \pm SD |
| Crystalloids, mL | Mean \pm SD |
| Synthetic colloid, mL | Mean \pm SD |
| Albumin, mL | Mean \pm SD |
| Urine output, mL | Mean \pm SD |
| Blood loss, mL | Mean \pm SD |
| Fluid balance, mL | Mean \pm SD |
| Temperature at the end of the surgery, °C | Mean \pm SD |

Continued

Table 2 Continued

| All patients (n=) | |
|-------------------------------|-------------|
| Transfusion of blood products | n/Total (%) |

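### A log-transformation is the only remedy for non-linearity in the PPC association model: it is undefined at zero PEEP and cannot represent a U-shape or a steepening rise in risk

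*SAP*

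**What the plan says.** The rule stands in the SAP under Primary outcome, within the predefined statistical analysis plan. Linearity on the log-odds scale is to be judged from a graph and, "if not present, a log-transformation will be performed". It belongs to the association analysis introduced there: "The impact of ventilatory variables on the development of PPC will be assessed using a generalised linear mixed-effect model". It covers every continuous predictor. The SAP names no spline, polynomial or other transformation. It gives no rule for zero or negative values and no second look at the fit after transformation.

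Three other places show which values the rule may meet:

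- **PEEP.** The Ventilatory variables subsection lists "PEEP levels, tidal volume size, respiratory rate" among the measurements. Under Primary outcome, PEEP is removed only from a secondary model: "Driving pressure will be considered in a sensitivity analysis, excluding PEEP, peak and plateau pressure". By implication it is in the main model.
- **CO2 insufflation pressure.** It is analysed over four time points. The first precedes insufflation and the last is "5 min after removal of pneumoperitoneum and return to supine".
- **Fluid balance.** Mock Table 2 lists "Fluid balance, mL" as an intraoperative characteristic.

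The final model uses repeated measurements, since "time of measurement will be included as a fixed effect together with the variables of interest", with centres and patients as random effects.

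**The concern.** Evaluating how ventilatory parameters relate to outcome is a stated aim of the study, and this is the model that answers it for PPC. The linearity rule takes effect once the graph shows a departure from a straight line, and it then prescribes one response whatever the departure looks like.

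That response can fail in two ways. For some predictors the log does not exist at values the data may contain, so the rule cannot be followed without a decision the SAP does not make. For some shapes the log exists but does not cure the problem the graph has just shown. In the first case an analytic choice is made after the data are seen. In the second, a real association may be missed or drawn with the wrong shape.

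**Working it through.** The SAP states no sample size, power or effect size for this model (the Sample size section describes a convenience sample), so there is no figure to reproduce. The check has three parts.

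**1. Where the log is undefined.** log(0) is minus infinity, and the log of a negative number, such as a fluid balance of -200 mL, does not exist. In R, the SAP's software, standard model fitting stops with an error on an infinite predictor. A negative value becomes a missing value and its row is dropped with a warning. For zero PEEP the analyst therefore meets an error and must choose between two repairs.

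- *Drop the rows.* The SAP does not say how often PEEP is zero. Assume 1000 patients with four readings each, so 4000 rows. If 2%, 5%, 10% or 20% of readings were zero, 4000 × (1 - share) leaves 3920, 3800, 3600 or 3200 rows. The lost rows are exactly the zero-PEEP readings.
- *Add a constant c.* The modelled step from 0 to 5 cmH2O relative to the step from 5 to 10 is [log(5+c) - log(c)] / [log(10+c) - log(5+c)]:

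| c | Ratio of steps |
|---|---|
| 0.01 | 9.0 |
| 0.1 | 5.8 |
| 0.5 | 3.7 |
| 1 | 3.0 |

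The constant, which nobody has specified, changes the relative weight of the zero-PEEP contrast threefold (9.0 / 3.0).

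**2. Which shapes a log can take.** For a term β·log(x), the slope is β/x and the second derivative is -β/x². The slope never changes sign, so a U-shape is out of reach. If risk rises with x (β > 0), the curve must flatten, so a rise that steepens is also out of reach. This part needs no assumption about the data.

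**3. What it could cost in power.** All inputs are assumptions except the two-sided 5% level and the background PPC rate of about 5%, which the SAP's Introduction gives for surgery in general. The assumed predictor resembles tidal volume (mean 8, SD about 1.4 to 1.5 mL/kg). With z the standardised predictor and m the location of the minimum, log odds = constant + b(z - m)². With N = 1000 and 5% PPC there are 1000 × 0.05 = 50 events. The models were single-level logistic regressions with likelihood-ratio tests.

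| Assumed truth | Log term | Restricted cubic spline |
|---|---|---|
| Strong U (b about 0.35), minimum at the mean | about 21-26% | about 98-99% |
| Weaker U (b = 0.2), minimum at the mean | about 13% | 51-55% |
| Weak U (b = 0.1), minimum at the mean | about 10% | about 14% |
| Weaker U (b = 0.2), minimum 1 SD below the mean | about 91% | 94-96% |

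For scale, at 2 SD from the minimum the odds ratio is exp(0.35 × 4) = 4.1 for the strong U and exp(0.2 × 4) = 2.2 for the weaker one.

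The reverse cost was checked too. If the truth is linear, power falls from 79% with a linear term to 71% with a 3-knot spline and 65% with a 4-knot spline.

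**The case against.** The case against has real weight on size and examples.

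- **The large power gap is close to a worst case.** It needs a strong effect and a minimum near the mean. With a small effect both methods do poorly, and with the minimum 1 SD off the mean both detect an association. The SAP nowhere says that any effect is U-shaped. This stands. Detecting an off-centre U with a log term does not, however, give the right shape.
- **The planned procedure was not simulated.** An analyst following the SAP would look at the graph first and would probably notice a U-shape. The planned model also has repeated rows and random effects, which the simulations left out. This stands as a limit on the figures. But once the graph is seen, the only response the SAP allows is still the log.
- **Patients lost.** A reader might infer that patients ventilated without PEEP would be silently excluded. The SAP does not support this. PEEP must first be judged non-linear, zero readings must occur, R stops with an error rather than dropping them, and any deletion is first of measurement rows. A whole patient would go only if every reading were zero or a patient-level covariate were not positive.
- **Insufflation pressure and fluid balance.** A reader might count both as failures of the rule. The SAP names the first only in the separate analysis over the four periods and the second only in a descriptive table. Neither is named as a PPC predictor, so they matter only if retained. A structural zero before insufflation or after desufflation would not be solved by a spline either.
- **Few events.** With about 50 events, extra spline terms are not free. This stands, and it favours 3 knots over 4.

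**Conclusion.** The point holds as a defect in a fixed rule. The log is the SAP's only remedy for non-linearity. It cannot be applied to PEEP of zero, or to any other retained predictor with zero or negative values, and it leaves a U-shaped or steepening relation misspecified. These conclusions follow from the text and from the mathematics of the log.

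The size is conditional. At 1000 patients and 5% PPC the power loss runs from large (about 21% against 99%) through moderate (13% against 51-55%) to small (91% against 94-96%), depending on the assumed strength and location of the U. It should not be read as an expected loss.

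The rule matters only where non-linearity is seen, and a log is adequate for a positive predictor whose risk rises and flattens. The primary outcome, PPC incidence reported as counts and percentages, is untouched. Severity is minor to moderate.

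**What to change.** Replace the rule under Primary outcome with: *Where the relation with the log odds is not linear, the predictor will be modelled with a restricted cubic spline (3 knots at fixed quantiles), tested jointly and shown as a curve with 95% CI; variables that can be zero or negative will not be log-transformed.* Keep the linear term where linearity holds.

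The cost is one sentence of SAP text, standard R code and one extra degree of freedom per non-linear predictor. Fitting a spline where the truth is in fact linear would lower power from about 79% to 71% in the assumed setting, and keeping linear terms where linearity holds limits that loss.

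### The main PPC model holds plateau or peak pressure fixed beside PEEP and, by inference, tidal volume, so their coefficients need not show how those settings relate to PPC

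*SAP*

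**What the plan says.** The purpose of the model is given in the SAP, 'Predefined statistical analysis plan', under 'Primary outcome': "The impact of ventilatory variables on the development of PPC will be assessed using a generalised linear mixed-effect model". In the final model "time of measurement will be included as a fixed effect together with the variables of interest", with centre and patient as random effects. Peak, plateau and driving pressure are expected to be strongly correlated, so "the main model will consider the variable with the higher amount of measurements between peak or plateau pressure". The one planned alternative is: "Driving pressure will be considered in a sensitivity analysis, excluding PEEP, peak and plateau pressure".

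The model's terms are not listed. That PEEP is in the main model follows from its removal in the alternative. That tidal volume is in both models is an inference: it is named as a ventilatory variable under 'Ventilatory variables' and is not among the exclusions. That section lists "Peak, plateau and driving pressure (defined as plateau minus positive-end expiratory pressure (PEEP)) and PEEP levels, tidal volume size, respiratory rate", and so also supplies the definition of driving pressure used below.

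**The concern.** Plateau pressure is not a separate exposure from PEEP and tidal volume. By the SAP's own definition it equals PEEP plus driving pressure, and driving pressure is tidal volume divided by static compliance. Holding plateau fixed changes what the other two coefficients mean:

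- At a given plateau, one more cmH2O of PEEP is one less cmH2O of driving pressure. The PEEP coefficient then carries the driving-pressure association with its sign reversed.
- At a given plateau and PEEP, driving pressure is fixed. A larger tidal volume per kg then reflects a more compliant respiratory system relative to predicted body weight (PBW), and any harm that tidal volume does through driving pressure has been adjusted away.

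The association between ventilatory parameters and outcome is a stated aim. The Introduction says that evidence on ventilatory strategy is insufficient and mentions reports that favour keeping normocapnia "despite the associated need for high tidal volumes". A null or protective tidal-volume coefficient, presented as an impact of ventilation, could be read as an answer to that question when it is not one.

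**Working it through.** The SAP gives no effect size, power or sample size for this model, so there is no planned figure to reproduce. The check is algebra followed by simulation.

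**Algebra.** From the SAP, driving pressure (DP) = plateau − PEEP. Suppose risk depends only on DP, with slope b, and PEEP is inert:

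log-odds = a + b·DP = a + b·plateau − b·PEEP + 0·(tidal volume)

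- PEEP odds ratio in the main model with plateau: exp(−0.10) = 0.905 for b = 0.10, and exp(−0.05) = 0.951 for b = 0.05. The truth is 1.00.
- Tidal-volume odds ratio in the same model: exp(0) = 1.00.
- Actual effect of 1 mL/kg more tidal volume: DP rises by PBW/compliance, which at the assumed means is 65/40 = 1.625 cmH2O. The odds ratio is exp(0.10 × 1.625) = 1.18. Averaged over patients it is 1.20, because stiff lungs contribute disproportionately.

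**Simulation.** 400,000 patients, one record each, ordinary logistic regression. All inputs are assumptions and none comes from the SAP: compliance 40 (SD 10) mL/cmH2O, tidal volume 8 (SD 1.3) mL/kg PBW, PBW 65 (SD 9) kg, PEEP 5 (SD 2) cmH2O, peak = plateau + 5 (SD 2), PPC risk 10% at mean log-odds. Where low compliance carries its own risk, it adds 0.2 or 0.4 log-odds per 10 mL/cmH2O. The true PEEP odds ratio is 1.00 in every row. VT is tidal volume.

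| Source of risk | True VT OR | No pressure term: VT / PEEP | Main, plateau: VT / PEEP | Main, peak: VT / PEEP | Sensitivity (DP, VT kept): VT |
|---|---|---|---|---|---|
| DP 0.10 | 1.203 | 1.204 / 0.998 | 0.997 / 0.903 | 1.025 / 0.915 | 0.997 |
| DP 0.05 | 1.097 | 1.091 / 1.000 | 0.997 / 0.952 | 1.010 / 0.957 | 0.997 |
| DP 0.10, low compliance 0.2 | 1.200 | 1.206 / 1.001 | 0.948 / 0.881 | 0.971 / 0.891 | 0.948 |
| DP 0.10, low compliance 0.4 | 1.194 | 1.200 / 1.000 | 0.889 / 0.850 | 0.921 / 0.866 | 0.889 |
| Low compliance 0.4 only | 1.000 | 0.995 / 0.997 | 0.890 / 0.941 | 0.906 / 0.949 | 0.890 |
| DP 0.10 and direct VT 0.10 | 1.317 | 1.325 / 0.999 | 1.104 / 0.903 | 1.126 / 0.910 | 1.104 |
| Direct VT 0.10 only | 1.105 | 1.108 / 1.001 | 1.107 / 1.000 | 1.096 / 1.000 | 1.107 |

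The no-pressure and sensitivity columns are from the plateau runs. With no effects at all, every odds ratio fell between 0.996 and 1.003, which shows the simulation error.

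The plateau results match the algebra. The sensitivity model avoids the PEEP artefact only by leaving PEEP out, and it still holds fixed the path through which tidal volume acts.

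**Does dropping the pressure term suffice?** Not if tidal volume follows lung stiffness. With tidal volume lowered by 0.5 mL/kg per 10 mL/cmH2O of lost compliance and DP at 0.10, the model without a pressure term gives a tidal-volume odds ratio of 1.080 (true 1.204). Adding compliance gives 1.217.

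**The case against.** **The model is partly reconstructed.** This stands as a limit. Tidal volume is inferred from a list that serves the descriptive repeated-measures analysis. The SAP also asks that covariates have "clinical relevance and no statistical association with other relevant variables", and it checks Pearson correlations among predictors generally, not only among the three pressures. Either rule could remove tidal volume or PEEP. But the first is written for covariates rather than the variables of interest, neither gives a threshold, and pairwise correlations do not show that plateau is built from PEEP, tidal volume and compliance together.

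**Tidal volume is not always the set variable.** This stands. SAP Table 3 includes pressure-controlled ventilation, in which pressure is set and tidal volume results. The identity still holds, but the remedy must take mode into account.

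**A reader might infer that the planned model must give a null or reversed answer.** The SAP does not support that. The distortion needs risk to run through driving pressure or low compliance. A purely direct tidal-volume effect is recovered without bias, and with both paths the estimate is attenuated but still on the harmful side (1.10 against 1.32).

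**A reader might infer that, at fixed plateau and PEEP, a larger tidal volume can only mean a more compliant lung.** That is too strong. Table 3 expresses tidal volume per kg of predicted weight, so a smaller predicted weight does the same. If peak is chosen, airway resistance enters as well.

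**A settings model is itself confounded if it bars compliance.** This stands, as the last check above shows. With DP at 0.08 and tidal volume lowered in stiff lungs, the tidal-volume odds ratio is 1.06 without compliance, and 1.01 if stiffness also adds risk. If an inert PEEP is raised in stiffer lungs, its odds ratio becomes 1.06 to 1.11.

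**The aim is observational association.** Also fair. Mutually adjusted associations are legitimate if labelled as such. The difficulty is calling them an impact while planning no model free of airway pressure.

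**Conclusion.** The point holds conditionally and should be fixed. As written, the main model adjusts PEEP, and by inference tidal volume, for a pressure that is partly made of them.

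If risk runs only through driving pressure, an inert PEEP takes an odds ratio of about 0.90 per cmH2O at 0.10 log-odds per cmH2O, or 0.95 at 0.05. A tidal volume whose true odds ratio is about 1.20 per mL/kg (1.10 at the smaller effect) shows 1.00. If low compliance also raises risk, the tidal-volume odds ratio falls to about 0.95, or 0.89 at the stronger assumed value. With peak pressure the distortion is slightly weaker.

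The direction follows from the SAP's own definition, and a larger sample does not remove it. The sizes rest on assumed inputs and on one record per patient without random effects.

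A reader might take this as a defect in the primary outcome. It is not: PPC incidence is a count and a percentage and does not depend on this model. Only the association aim is affected.

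**What to change.** In the SAP, 'Primary outcome':

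1. List the terms of each model.
2. Add a ventilator-settings model with tidal volume, PEEP, respiratory rate, FiO2 and confounders, and no peak, plateau or driving pressure. Report it with and without respiratory-system compliance, preferably the T1 value taken before insufflation. Take ventilation mode into account, by adjustment or by separate estimates, because pressure is the set variable in pressure-controlled mode.
3. Keep the peak-or-plateau model and the driving-pressure model for statements about pressure only.
4. State that tidal-volume and PEEP coefficients from any model containing an airway pressure are not read as associations of those settings with PPC.
5. Replace 'impact' with 'association'.

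The cost is SAP wording and one or two extra models on variables already planned for collection. Residual confounding by lung stiffness will remain. The version adjusted for static compliance will lose patients without a plateau reading.
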